## 15.0 REGULATORY AND REPORTING REQUIREMENTS

- The descriptions and grading scales found in the revised NCI Common Terminology Criteria for Adverse Events (CTCAE) version 3.0 will be utilized for adverse event reporting. All appropriate treatment areas should have access to a copy of the CTCAE version 3.0. A list of adverse events that have occurred or might occur can be found in Sections of Pharmaceutical Information for SUNITINIB and BCG.
- SAE Definition. A SAE is any adverse event, without regard to causality, that is life-threatening or that results in any of the following outcomes: death; in-patient hospitalization or prolongation of existing hospitalization; persistent or significant disability or incapacity; or a congenital anomaly or birth defect. Any other medical event that, in the medical judgment of the Principal Investigator, may jeopardize the subject or may require medical or surgical intervention to prevent one of the outcomes listed above is also considered an SAE. A planned medical or surgical procedure is not, in itself, an SAE. Also specifically excluded from this definition of SAE is any event judged by the Principal Investigator to represent progression of the malignancy under study, unless it results in death within the SAE Reporting Period.
- SAE Reporting Period. The SAEs that are subject to this reporting provision are those that occur from after the first dose of the study drug through 28 days after discontinuation of study drug(s).

### 15.1 EXPEDITED ADVERSE EVENT REPORTING

- Expedited reports are submitted via an adverse event reporting form to the IRB which will be created as part of the clinical report forms used for the study. The adverse event will also be reported to Pfizer via fax as well as a Medwatch form. Those AEs that do not require expedited reporting must be reported in routine study data submissions. AEs reported in

expedited review must **also** be reported in routine study data submissions including the Data and Safety Monitoring report.

- Expedited Reporting Guidelines –Reporting Requirements for Adverse Events That Occur Within 28 Days of the Last Dose of the Investigational Agent.

	Grade 1	Grade 2	Grade 2	Grade 3		Grade 3		Grades 4 & 5 	Grades 4 & 5 
	Unexpected & Expected	Unex- pected	Expected	Unexpected with Hospitalization	without Hospitalization	Expected with Hospitalization	without Hospitalization	Un-expected	Expected
Unrelated Unlikely	Not Required	Not Required	Not Required	10 Calendar Days	Not Required	10 Calendar Days	Not Required	10 Calendar Days	10 Calendar Days
Possible Probable Definite	Not Required	10 Calendar Days	Not Required	10 Calendar Days	10 Calendar Days	10 Calendar Days	Not Required	24-Hour; 5 Calendar Days	10 Calendar Days

 Adverse events with attribution of possible, probable, or definite that occur greater than 28 days after the last dose of treatment require reporting as follows:

IRB 24-hour notification followed by complete report within 5 calendar days for:

- Grade 4 and Grade 5 unexpected events
- IRB 10 calendar day report:
- Grade 3 unexpected events with hospitalization or prolongation of hospitalization
- Grade 5 expected events

 Although an IRB 24-hour notification is not required for death clearly related to progressive disease, a full report is required as outlined in the table.

**Note: All deaths on study must be reported using expedited reporting regardless of causality.**

**Attribution to treatment or other cause should be provided.**

- Expedited AE reporting timelines defined:
  - “24 hours; 5 calendar days” – The investigator must initially report the AE within 24 hours of learning of the event followed by a complete report within 5 calendar days of the initial 24-hour report.
  - “10 calendar days” - A complete report on the AE must be submitted within 10 calendar days of the investigator learning of the event.

- Any medical event equivalent to CTCAE grade 3, 4, or 5 that precipitates hospitalization (or prolongation of existing hospitalization) must be reported regardless of designation as expected or unexpected and attribution.
- Any event that results in persistent or significant disabilities/incapacities, congenital anomalies, or birth defects must be reported.
- Use the protocol number and the protocol-specific patient ID provided during trial registration on all reports.
- **Expected adverse events** are identified in Sections above.
- For **Hospitalization** only – Any medical event equivalent to CTCAE grade 3, 4, or 5 that precipitated hospitalization (or prolongation of existing hospitalization) must be reported regardless of designation as expected or unexpected and attribution.

### **Serious Adverse Event (SAE) Reporting to Pfizer and The University of Michigan**

Within 24 hours of first awareness of the event (immediately if the event is fatal or life-threatening), the Principal Investigator at the site of the event will report to the University of Michigan any Serious Adverse Event ("SAE," as defined above) that occurs during the SAE reporting period (from after the first dose of the study drug through 28 days after discontinuation of study drug).

Within 24 hours of first awareness of the event (immediately if the event is fatal or life-threatening), Principal Investigator will report to the Pfizer by facsimile any Serious Adverse Event ("SAE," as defined below) that occurs during the SAE reporting period (as defined below) in a Study subject assigned to receive the Pfizer Product. Principal Investigator will report such SAEs using an FDA MEDWATCH form and the Serious Adverse Event Fax Cover Sheet provided by Pfizer. SAEs should be reported as soon as they are determined to meet the definition, even if complete information is not yet available.

**SAE Reporting Period.** The SAEs that are subject to this reporting provision are those that occur from after the first dose of the Pfizer Product through 28 days after discontinuation of the Pfizer Product.

**Follow-Up Information.** Institution will assist Pfizer in investigating any SAE and will provide any follow-up information reasonably requested by Pfizer.

**Regulatory Reporting.** Reporting an SAE to Pfizer does not relieve Institution of responsibility for reporting it to regulatory authorities, as required.

## **15.2 DATA REPORTING**

## [name], Phase II Study of BCG followed by Sunitinib for High risk NMIBC

- All data must be entered in “real time” such that all data are current. A study database will be created by the Clinical Trials Office of the Department of Urology for this purpose.

### Responsibility of the Principal Investigator

- The Principal investigator will be the single liaison with Pfizer. The Principal Investigator is responsible for the coordination, development, submission, and approval of the protocol as well as its subsequent amendments. The protocol must not be rewritten or modified by anyone other than the Principal Investigator. There will be only one version of the protocol.
- All reporting requirements to the IRB / Pfizer are the responsibility of the Principal investigator.
- The Principal Investigator is responsible for the timely review of Adverse Events (AE) to assure safety of the patients.
- The Principal Investigator will be responsible for the review of and timely submission of data for study analysis.
- Any manuscripts reporting the results of this clinical trial will be provided to Collaborator(s) for advisory review and comment prior to submission for publication. Collaborator(s) will have 14 days from the date of receipt for review. Copies of abstracts will be provided to Collaborator(s) for courtesy review as soon as possible prior to submission, but in any case, prior to presentation at the meeting or publication in the proceedings.

## 16.0 STATISTICAL CONSIDERATIONS

### 16.1 STUDY DESIGN/ENDPOINTS

The primary objective of this trial is to estimate the complete response rate in patients with high-risk non-muscle invasive bladder cancer treated with intravesical bacillus Calmette Guerin followed by daily oral sunitinib for 4 weeks as assessed by urine cytology, cystoscopic biopsy, and exam under anesthesia. If the response rate is 55% or less, there would be little interest in pursuing this therapy in further studies. In this case, we would like to terminate the trial early and consider a new therapy. If the response rate is 75% or more, further study would be proposed based on the estimates produced in this trial. To minimize the number of patients treated, the Minimax two-stage accrual design [Controlled Clinical Trials 10:1-10 1989] has been adopted.

## [name], Phase II Study of BCG followed by Sunitinib for High risk NMIBC

We will accrue 24 high-risk non-muscle invasive bladder cancer patients. If less than 16 responses are seen, the trial will stop. If 16 or more responses are seen, an additional 12 patients will be entered. If 25 or more of the 36 evaluable patients achieve a complete response, then further studies will be proposed.

This trial design provides 80% statistical power at the 5% significance level. If the response rate was as low as 55%, there would be a 83% chance of stopping the trial after just 24 patients and only a 4.9% chance of going on to stage two (false positive error). However if the true response rate was 75%, there would only be a 12% chance of stopping the study early and a 19.9% chance of rejecting the therapy (false negative error). Evaluable patients will include all patients who receive at least one dose of sunitinib. Patients who are removed from the study before treatment with sunitinib will be replaced.

### 16.2 ANALYSES

The primary endpoint for this study will be the complete response rate. This rate will be reported along with 95% confidence intervals.

This study has several secondary endpoints. Response rates at 6 months will be reported with 95% confidence intervals for patients with an intact bladder. Kaplan-Meier estimates will be used to describe recurrence-free survival, including 2-year recurrence-free survival estimates. Toxicity of this therapy will be described, both overall and by grade. Toxicity rates will be tabulated by type and category.

Correlation of changes in VEGF, VEGFR, p53, and other cytokine expression to response will be explored. Markers will be grouped based on terciles of the distribution. Bivariate relationships between the expression level and response status will be assessed with the Mantel-Haenszel chi-square test. Potential analyses will include logistic regression with an outcome of response and Kaplan-Meier methods for time to recurrence. Differences in time to recurrence by expression level will be illustrated by Kaplan-Meier plots and tested using the log-rank test. Due to the sample size and the number of factors we will be statistically testing, these analyses will be considered exploratory until confirmed in a larger, independent, clinical trial.

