Urine represents an ideal medium to evaluate response to therapy in patients with localized bladder cancer as it may directly indicate the response to therapy. Further, based on preliminary results described previously, serum levels of biomarkers may also be informative. We will investigate the effect of BCG and sunitinib therapy on urinary and serum levels of various VEGFs, soluble VEGF receptors, and cytokines IL8, IL6, interferon gamma, and interferon alpha. Measurements will be performed using commercially-available ELISA kits. Utility of additional biomarkers (e.g., PDGF, [35]) will be evaluated on a pilot basis.

Correlation of changes in VEGF, VEGFR, p53, and other cytokine expression to response will be explored. Markers will be grouped based on terciles of the distribution. Bivariate relationships between the expression level and response status will be assessed with the Mantel-Haenszel chi-square test. Logistic regression will be used to assess the effect of combining markers to predict response. Differences in time to recurrence by expression level will be illustrated by Kaplan-Meier plots and tested using the log-rank test. Due to the sample size and the number of factors we will be statistically testing, these analyses will be considered exploratory until confirmed in a larger, independent, clinical trial.

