### **Procedures and Methods:**

## [name], Phase II Study of BCG followed by Sunitinib for High risk NMIBC

- Voided urine and serum will be obtained as outlined on the study calendar. If BCG is given locally no specimens need to be obtained at Week 1 and Week 6 visits. In addition, a bladder biopsy will be obtained at the 3 month endoscopic biopsy to assess response. These specimens will only be obtained for the first study cycle.
- Urine will be kept on ice until it can be centrifuged in the research laboratory. The urine and pellet will aliquoted into separate tubes, codes, and stores at -80°C in the research laboratory.
- Tissue will be collected at the time of bladder biopsy at 3 months and processed with formalin fixation and paraffin-embedding in the Pathology Department, following the standard operating procedure of the previously approved University of Michigan Bladder Cancer (Tissue/Blood/Urine/Data) Bank (IRB 1996-0379). Blocks and tissue sections will be stored in research lab until processed.
- Tissue biomarker standardization will be performed by microscopic evaluation in collaboration with a pathologist. Each assay will be performed with positive and negative control tissues from comparisons. Responses will be scored based on the number of cells staining positive and the level of positivity (0-3+).
- Urine biomarker standardization will be based on urine creatinine measurements.

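### Cutting the ELISA markers into terciles before testing costs the exploratory marker analyses roughly 10 points of power at 36 patients, under stated assumptions, and a wording change recovers most of it

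*Combined protocol and SAP*

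**What the plan says.** Sections 12.0 and 16.2 both put the grouping first: "Markers will be grouped based on terciles of the distribution". The tests follow. For response: "Bivariate relationships between the expression level and response status will be assessed with the Mantel-Haenszel chi-square test". For recurrence: "Differences in time to recurrence by expression level will be illustrated by Kaplan-Meier plots and tested using the log-rank test". The documents give no reason for choosing terciles, and they specify no rank-based or continuous bivariate test.

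On measurement, section 12.0 says of the urine and serum markers: "Measurements will be performed using commercially-available ELISA kits". Tissue markers are different: "Responses will be scored based on the number of cells staining positive and the level of positivity (0-3", the scale ending at 3+.

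Section 12.0 commits to a multi-marker model: "Logistic regression will be used to assess the effect of combining markers to predict response". Section 16.2 lists logistic regression only as a potential analysis. Neither section says whether markers enter that model as terciles or as measured values.

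Both sections limit the status of the work: "these analyses will be considered exploratory until confirmed in a larger, independent, clinical trial". No power, effect size or significance level is stated for any marker analysis.

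**The concern.** A tercile code treats every value within a third of the sample as equal. With 36 patients the groups hold 12 each; if the trial stops after stage 1, they hold 8. The cut-points come from the sample itself. For an assay that returns a concentration, this throws away ordering and distance that have already been measured.

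What is at stake is the chance of picking up a real marker signal. Section 2.6 says the specimens will be used to look for candidate biomarkers of response, so a missed association is the main cost. The exploratory label limits what may be claimed from a positive result, but it does not restore sensitivity lost through coding.

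**Working it through.** **Inputs from the documents.** Section 16.1: at most 36 evaluable patients, 24 in stage 1, stop with fewer than 16 responses, success with 25 or more of 36, rates of 55% and 75%. Section 16.2: tercile coding and the Mantel-Haenszel test. Section 12.0: ELISA measurement.

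**The plan's own figures.** There are none for the markers. The two-stage design that sets the sample size does reproduce. By exact binomial sums, early stopping is 82.7% at a 55% rate and 12.1% at 75%, and the probability of 25 or more responses after continuing is 4.93% and 80.1%. So 36 patients with a 25/11 split is a fair reference case: it is the success boundary.

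**Information kept by terciles (assumed: normal marker, linear effect, 1-df trend with equally spaced scores).** Let X be standard normal and S = −1, 0, 1 by tercile.
- Cut-point c = Φ⁻¹(2/3) = 0.4307, with density φ(c) = 0.3636.
- Cov(X, S) = 2φ(c) = 0.7272, and Var(S) = 2/3.
- Efficiency = 0.7272² / (2/3) = 0.793, a loss of 20.7%.
- 36 × 0.793 = 28.6, so about 7.4 patients are lost. At stage 1, 24 × 0.793 = 19.0.

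**Other assumed shapes, effect linear on the measured scale.**

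| Marker shape | Loss |
|---|---|
| Uniform, or effect linear in ranks (efficiency 8/9) | 11% |
| Normal | 21% |
| Logistic | 26% |
| t, 5 df | 31% |
| Log-normal, log-SD 0.5 | 35% |
| Exponential | 39% |
| Log-normal, log-SD 1 | 64% |

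If a log-normal marker acts linearly on the log scale, the tercile loss is again 21%. Untransformed values then keep σ²/(exp(σ²) − 1). That is 0.25/0.284 = 88% for log-SD 0.5 and 1/1.718 = 58% for log-SD 1, the latter below the 79% of terciles.

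**Power for an assumed 1 SD shift, 25 responders and 11 non-responders, two-sided 5%.** Normal approximation: the noncentrality is √(25 × 11/36) = 2.764 continuous and 2.764 × √0.793 = 2.462 with terciles. Power is then Φ(2.764 − 1.96) = 79% against Φ(2.462 − 1.96) = 69%, a gap of 10 points. Simulation of the (n − 1)r² test gives slightly lower levels and the same gap: terciles 65 to 66%, continuous 76%, ranks 73 to 74%. Null rejection rates at this split are all between 4.6% and 5.0%, so the comparison is fair.

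**Second model.** Logistic response, 36 patients, 69% responding, odds ratio 2.7 per SD: continuous 67%, ranks 65%, tercile trend 57%, tercile 2-df test 49%. For log odds ratios of 0.5, 0.8, 1.0, 1.2 and 1.5 per SD, the trend test gives up 4, 9, 10, 10 and 8 points against continuous.

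**The case against.** The strongest answer is that nothing the trial decides depends on these tests. The correlative objective is separate from the primary and secondary ones, the go/no-go rule counts complete responses only, and no operating characteristic is claimed for the markers. This stands and holds the point to minor.

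Terciles also have merits: they resist outliers and assume no particular functional form. That stands in part. A continuous analysis on the wrong scale can do worse (58% against 79% above), so the remedy must be ranks or logs, not raw values.

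A reader might infer more than the documents support in five ways.

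- **A fifth of the information is lost, as a fact about this trial.** The documents give no assay distributions. The 21% belongs to a normal, linear, 1-df case, and other assumptions move it.
- **The power cost is about 17 points.** With 27 responders and 9 non-responders, simulation gives about 53% with terciles against 70% continuous. The tercile test there rejects only about 3.2 to 3.6% under the null, so part of the gap is discreteness. At 20/16 it rejects about 6.5 to 6.7%, which makes that gap of about 4 points too small. Neither contrast measures information loss cleanly.
- **Every marker could be analysed as continuous.** Tissue p53 and HIF1a are scored semi-quantitatively, so ordinal handling may be all that is available, and ties may prevent equal thirds.
- **The logistic model also uses terciles.** Its marker scale is simply not stated.
- **All 36 patients will contribute.** Thirty-six is the maximum, the trial may stop at 24, and "If BCG is given locally no specimens need to be obtained at Week 1 and Week 6 visits".

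**Conclusion.** The point holds, as a minor one, for the bivariate and log-rank tests of the ELISA markers. Tercile coding loses about 21% of the information for a normal or log-normal marker with a linear effect on the normal scale. The loss is about 11% if the effect is linear in ranks, and more if a skewed or heavy-tailed marker acts linearly on its raw scale. At the maximum sample size and the 25/11 split, the cost is roughly 10 points of power for an assumed 1 SD shift. These sizes rest on the stated assumptions and not on any figure in the documents.

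They also assume a 1-df trend test. The plan does not say whether the log-rank comparison uses the ordering of the groups. In the response simulation, ignoring the order took tercile power from 57% to 49%.

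**What to change.** Reword the marker paragraphs in sections 12.0 and 16.2 as follows.

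- **Response.** Test each ELISA marker change with a Wilcoxon test, or with logistic regression per SD of the log-transformed value. Choose one in advance.
- **Time to recurrence.** Use Cox regression per SD of the log-transformed marker.
- **Multi-marker logistic model.** State that ELISA markers enter on that same scale, and make the two sections agree on whether the model is planned or only potential.
- **Tissue score.** Analyse the 0 to 3+ score as ordinal, on its own levels.
- **Terciles.** Keep them for the Kaplan-Meier display.

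Untransformed concentrations should not be used.

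The cost is wording only: no extra patients, specimens or visits. The price in assumptions is a monotone relation for ranks or a log-linear one for the models, and the tercile plots give a rough check of either. The exploratory label should stay.

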### 16.3 PATIENT ACCRUAL

Based on previous experience, the accrual to this trial is expected to be 3 eligible patients per month. Thus, the accrual period for the first stage is expected to be 8 months. The second stage is expected to take an additional 3 months to accrue the final 12 patients.

### 16.4 REPORTING AND EXCLUSIONS

**16.4.1 EVALUATION OF TOXICITY.** All patients will be assessable for toxicity from the time of their first treatment with study drug.

**16.4.2 EVALUATION OF RESPONSE.** All eligible patients included in the study must be assessed for response to treatment, even if there are major protocol treatment deviations or if they are taken off study. Evaluation of response will be performed as outlined in Section 14 of the protocol.

All of the patients who met the eligibility criteria and receive at least one dose of sunitinib should be included in the main analysis. All conclusions should be based on all eligible patients. Sub analyses may then be performed on the basis of a subset of patients, excluding those for whom major protocol deviations have been identified (e.g., early death due to other reasons, early discontinuation of treatment, major protocol violations, etc.). However, these subanalyses may not serve as the basis for drawing conclusions concerning treatment efficacy, and the reasons for excluding patients from the analysis should be clearly reported. The 95% confidence intervals should also be provided.

## **17. DATA MANAGEMENT AND MONITORING:**

**17.1 DATA COLLECTION/ENTRY:** Clinical report forms will be developed by the principal investigator and study coordinator for data collection and entered into a password protected database which will be created at the initiation of the trial.

Adverse events, including all toxic effects of treatment, will be tabulated, individually summarized by body system and to severity or toxicity grade. See section 15 for adverse event reporting.

